In this pilot study, we will enroll 19 individuals with chronic motor incomplete or SCI. The **primary objectives** are 1) to examine the feasibility of an 8-week walk-training program and 2) to examine the potential association between changes in resting and exercise heart rate and changes in three major factors after 8-week walk-training in individuals with chronic SCI. The **secondary objective** is to collect pilot data before and after the 8-week walking exercise program for evaluating changes in risk markers of CVD in study participants.

Aim#1: To examine feasibility (recruitment, perception, compliance, retention, and walking performance) of an 8-week walk-training program in patients with chronic SCI.

Aim#2: To examine correlations between changes in four factors (muscle activity, autonomic function, spasticity, and lung capacity) and changes in resting and exercise heart rate after the walk-training program in individuals with chronic SCI. Primary hypothesis: Decreases in resting and exercise heart rate after the

walk-training will show significant correlations with increased leg muscle activity, which will be stronger than its correlations with an changes in changes in cardiac autonomic function, leg muscle spasticity, or vital lung capacity.

Aim#3: To investigate the effects of an 8-week walk-training on lipid profile, the level of glycated hemoglobin (HbA1c), and the levels of pro-inflammatory markers in individuals with chronic SCI.

Secondary hypothesis: Compared to baseline measures, the 8-week walk-training program will decrease the levels of total cholesterol, low-density lipoprotein cholesterol and HbA1c, will increase the level of high-density lipoprotein cholesterol and reduce the levels of C-reactive protein and interleukin-6.

Exploratory aims: To investigate the effects of the walk-training program on lower limbs muscle strength and spasticity, functional independence, the level of depression, anxiety and stress, and health-related quality of life in individuals with chronic SCI.

B. Background and Significance

B.1. An Overview of Spinal Cord Injury (SCI)

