We propose a pilot study to examine whether the increased leg muscle activities after a walk-training program contribute significantly to the improved cardiovascular health as indicated by heart rate adaptation. Cardiovascular disease (CVD) has a high prevalence rate (30%-50%) and is a leading cause of death among people with SCI [5, 11, 12][3]. For instance, a cohort study that followed individuals with SCI for five years after discharge from inpatient rehabilitation found that 37% individuals died due to cardiovascular causes [14]. Lack of physical activity/exercise and prolonged sitting in people with SCI is significantly associated with increased risk of CVD [17]. However, aerobic exercise using arm cycling or FES-leg cycling has shown inconsistent results on risk factors of CVD in SCI survivors. Arm cycling targets only upper limb muscles, which does not provide sufficient challenge to the cardiovascular system [97, 99]. FES-leg cycling is limited as patients often report muscle fatigue due to frequent stimulation [79, 95, 96], and aggravate the symptoms of autonomic dysreflexia particularly in those with SCI above T6 [106]. Both arm cycling and FES-leg cycling exercises are performed in a sitting position which may not provide sufficient stress to the cardiovascular system. As an alternative, upright walking using BWSTT has shown preliminary results of improving cardiovascular function in individuals with incomplete or complete SCI [79, 97, 99-102]. BWSTT induced leg muscle activities in a similar way to those seen in healthy individuals during walking [116]. However, the amplitude of the induced leg muscle EMG activities in persons with complete SCI was much lower compared to that in healthy individuals [117]. It is unknown how significantly the increased leg muscle activities after a period of walk-training can help to improve cardiovascular health. It is important to determine the extent that the increased leg muscle activities after a walk-training program can contribute to the heart rate adaptation, a reliable indication of improvement in cardiovascular fitness, in comparison to the contribution by other factors including changes in autonomic function, muscle spasticity, and lung capacity. The findings of the proposed study will help us to better understand the underlying mechanism of walk-training program on cardiovascular health. Clinically, such findings will help to guide clinical practice in rehabilitation for patients with chronic SCI on issues such as setting up priorities in patient's training.

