
In addition, there is still limited evidence about the effects of upright walk-training on risk markers of CVD in individuals with chronic SCI. Furthermore, previous studies have not investigated the effects of walk-training on risk markers of CVD in individuals with motor complete SCI. The influence of walk-training on

the pro-inflammatory markers has also not been studied in both incomplete and complete SCI. To explore those issues would further extend our knowledge to better understand the benefits of walking exercise in individuals with chronic SCI.

II. Research Plan and Design

A. Study Objectives:

The **primary objectives** are 1) to examine the feasibility of an 8-week walk-training program and 2) to examine the potential association between changes in resting and exercise heart rate and changes in four major factors after 8-week walk-training in individuals with chronic SCI. The **secondary objective** is to collect pilot data before and after the 8-week walking exercise for evaluating changes in risk markers of CVD in study participants.

B. Study Type and Design:

The proposed study is a pilot, single group, pre- and post-clinical study design for gathering feasibility and preliminary data for preparing a subsequent future clinical trial. At the initial contact with a study candidate, a phone screening will be conducted by a member of our research team to determine whether an individual is qualifying for the study. An eligible participant will receive BWSTT with assistive training device three sessions a week for eight weeks (a total of 24 sessions). Outcome measures will be taken at baseline and after completion of the walk-training program.

C. Sample size, statistical methods, and power calculation

In this pilot study, we focus more on feasibility issues. We will analyze the data of the study to find trends and to gather pilot data for preparing a future trial. Thus, we will recruit a total of 19 participants.

We have calculated sample size for one factor based on specific aim#2. With power of 80% and significance level of 0.1, we need 15 participants to find a significant correlation of ($r = 0.6$) between the one factor and the outcome variable. Considering drop out of 20 %, we will recruit a total of 19 participants.

D. Subject Criteria (See Vulnerable Populations appendix, if applicable):

a. *Inclusion criteria:*

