Statistical analysis will be conducted using SPSS statistical software. Descriptive statistics of frequency, mean, and standard deviation will be generated on the data collected during the study. Assumption of normal and variance of data will be assessed using Shapiro-Wilk test and Brown-Forsythe Levene test, respectively. For *primary hypothesis*, first, we will conduct the simple linear regression to determine whether there is a linear relationship between each factor and the outcome measure, which heart rate adaptation. If it is true that more than one factor is correlated

with outcome measure. As an Exploratory manner, we will conduct multiple linear regression to identify contribution of these factors to outcome measure and determine the factor that is strongly contributed to outcome measure based on contribution other factors. The level of significance for multiple regression will be set at 0.1 due to small sample of this pilot study. For *secondary hypothesis and exploratory aims*, the paired sample t-test will be utilized to assess difference in outcome measures pre- and post-training. The level of significance for paired-sample test will be set at 0.05.

B. Outcome:

Aim#1 expected results: For recruitment rate, we expect that one of every four candidate participants who are screened eligibility will enroll in the study (ratio of recruitment rate 4:1) as described in a past study in individuals with SCI.[183] For perception, we expect that participants will be satisfied with walk-training program in regard to time duration of walk-training and use of the assistive training device and time needs to step the assistive training device, and safety and comfortability of training. For compliance, we expect that participants will complete more than 80% of total training sessions. For retention, we expect that drop out during the study will be less than 20%. In regard to walking performance, we expected increase time of walk-training, treadmill walking speed, the number of stepping per session throughout training period.

Aim# 2 expected results: We expect that decreases in resting and exercise heart rate after 8 weeks of walking will show significant correlation with increased leg muscles activity, which will be stronger than its correlations with changes in cardiac autonomic function, leg muscle spasticity, or vital lung capacity

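### The primary hypothesis ranks leg muscle activity above three other factors, but the planned analysis tests each factor only against zero and never estimates a difference between correlations

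*Protocol*

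**What the plan says.** Aim 2 is one of the two primary objectives. Its primary hypothesis, in Protocol section I.A, has two parts. Decreases in resting and exercise heart rate will correlate significantly with increased leg muscle activity, and that correlation is one "which will be stronger than its correlations with an changes in changes in cardiac autonomic function", leg muscle spasticity or vital lung capacity. Section V.B repeats the second part as the expected result for Aim 2: "which will be stronger than its correlations with changes in cardiac autonomic function, leg muscle spasticity, or vital lung capacity".

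Section V.A fixes the analysis for the primary hypothesis in two steps.

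- Step 1: "we will conduct the simple linear regression to determine whether there is a linear relationship between each factor and the outcome measure".
- Step 2 has the trigger "If it is true that more than one factor is correlated" with the outcome. Then: "As an Exploratory manner, we will conduct multiple linear regression to identify contribution of these factors to outcome measure", and the factor that contributes strongly, given the others, is to be identified. The significance level for this step is 0.1.

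Section II.C sizes the study for one factor: a correlation of 0.6, 80% power and level 0.1 give 15 evaluable participants, or 19 with 20% dropout.

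**The concern.** Step 1 answers the first part of the hypothesis. Nothing in V.A answers the second.

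- If EMG alone is significant, step 2 does not run. The comparative statement then rests on one result being significant and the others not, which is not evidence that the correlations differ.
- If several factors are significant, step 2 gives partial contributions. Without an estimated difference, the comparison rests on rank. Partial contributions also answer a different question from the one in I.A and can reverse the order of the correlations.

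Section I.C says that "such findings will help to guide clinical practice in rehabilitation for patients with chronic SCI on issues such as setting up priorities" in training. A ranking that carries no uncertainty is a weak basis for that, and for choosing the target of the future trial.

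**Working it through.** **1. The Protocol's own figure.** Fisher z for one correlation of 0.6, two-sided 0.1, 80% power: n = ((1.645 + 0.842)/atanh 0.6)² + 3 = (2.487/0.693)² + 3 = 15.87. Simulating the exact t-test gives power of 77.7% at n = 14 and 80.6% at n = 15, so 15 is the smallest adequate number. Dropout: 15/0.8 = 18.75, so 19. The sample size is right for one correlation against zero and is not disputed.

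**2. One worked sample.** Take observed correlations of 0.6 (EMG) and 0.3 (a rival), with 0.3 between the two factors and n = 15.

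- Each against zero, t = r√((n−2)/(1−r²)): EMG 0.6 × √(13/0.64) = 2.70; rival 0.3 × √(13/0.91) = 1.13. The critical value on 13 df is 1.77, so EMG is significant and the rival is not.
- The difference, by Williams' test for two correlations sharing a variable: t = (r₁−r₂)√{(n−1)(1+r₁₂)/[2((n−1)/(n−3))D + r̄²(1−r₁₂)³]}, where r̄ is the mean of r₁ and r₂, and D = 1 − r₁² − r₂² − r₁₂² + 2r₁r₂r₁₂ = 1 − 0.36 − 0.09 − 0.09 + 0.108 = 0.568. So t = 0.3 × √{18.2/(1.325 + 0.069)} = 1.08, against 1.78 on 12 df.

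V.A would show EMG significant alone, yet the data do not separate the two correlations.

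**3. How often V.A favours EMG when all four factors are equal.** The Protocol gives no rival or inter-factor correlations, so these are assumed: equal true r of 0.3–0.5 and inter-factor r of 0–0.5. Simulation is multivariate normal, n = 15, two-sided 0.1, one outcome, 100,000 replicates per case. The joint model contains the significant factors and ranks them by standardised coefficient. The case r = 0.5 with inter-factor 0 is infeasible, because 4 × 0.5² = 1 leaves no residual variance. Figures are percentages of trials.

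| r / inter-factor r | EMG significant and largest | EMG only significant | More than one significant | EMG first in joint model | V.A end to end | Same, coefficient p<0.1 |
|---|---|---|---|---|---|---|
| 0.3 / 0 | 19.2 | 10.6 | 34.4 | 8.6 | 19.2 | 18.0 |
| 0.3 / 0.3 | 17.2 | 8.3 | 35.2 | 8.9 | 17.2 | 13.6 |
| 0.3 / 0.5 | 15.4 | 6.7 | 34.8 | 8.7 | 15.5 | 10.2 |
| 0.4 / 0 | 23.3 | 7.6 | 62.8 | 15.6 | 23.3 | 22.4 |
| 0.4 / 0.3 | 21.3 | 6.8 | 58.1 | 14.4 | 21.2 | 16.8 |
| 0.4 / 0.5 | 19.7 | 5.8 | 55.1 | 14.0 | 19.8 | 12.1 |
| 0.5 / 0.3 | 23.7 | 3.7 | 81.3 | 20.1 | 23.8 | 19.8 |
| 0.5 / 0.5 | 22.9 | 3.7 | 76.8 | 19.3 | 23.0 | 14.2 |

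End to end means EMG is the only significant factor or comes first in the joint model. By symmetry some factor is named strongest in 4 × 15.5 = 62% to 4 × 23.8 = 95% of trials. In the same cases Williams' test falsely favours EMG in 4.5–5.0% per rival, and in 0.5–0.7% against all three.

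**4. Partial contribution can reverse the order.** Let heart rate correlate 0.5 with EMG and 0.4 with each rival. Let EMG correlate 0.5 with spasticity and with vital capacity, let those two correlate 0.3, and let autonomic function be uncorrelated with the rest. The autonomic coefficient is then 0.40. Writing b for spasticity and vital capacity, β(EMG) + b = 0.5 and 0.5β(EMG) + 1.3b = 0.4, so b = 0.1875 and β(EMG) = 0.3125. EMG has the largest correlation but not the largest coefficient.

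**5. What a direct comparison can deliver at n = 15.** Williams' test, two-sided 0.1, true EMG r = 0.6, inter-factor r of 0 / 0.3 / 0.5:

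| Rival r | Power against one rival (%) | Power against all three (%) |
|---|---|---|
| 0 | 53.8 / 69.0 / 84.4 | 29.3 / 45.0 / 66.5 |
| 0.3 | 22.4 / 28.0 / 35.1 | 7.5 / 10.0 / 14.0 |
| 0.4 | 14.8 / 17.6 / 21.0 | 4.1 / 5.1 / 6.2 |

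A 90% Fisher-z MOVER interval for the difference has coverage of 89.6–90.6% and a median width of 0.77–1.13.

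**The case against.** The strongest reply is that V.A does compare the factors. Section I.C frames the question as contribution, "in comparison to the contribution by other factors including changes in autonomic function, muscle spasticity, and lung capacity", and step 2 is meant to find the leading contributor. On that reading the reversal example shows a different estimand rather than an error. This explains step 2 but does not rescue the hypothesis. I.A and V.B word the comparison as correlations, step 2 is exploratory, and it does not run when EMG alone is significant.

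A second reply is that V.A never says when EMG would be declared stronger, so the simulated rule is an assumption, and an SAP not at hand might supply one. It is also assumed that only significant factors enter the joint model; the text could mean all four. Both caveats stand for the percentages. They do not touch the gap itself: the Protocol names the analysis for this hypothesis, and that analysis leaves out the comparison.

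Third, 15.5–23.8% lies below the 25% chance of ranking first, and ranking is informative when EMG really is stronger. EMG is significant and largest in 55% of trials at 0.6 versus 0.4 (inter-factor 0.3) and in 69% at 0.6 versus 0.3 (inter-factor 0.5), where the all-three comparison succeeds in 5% and 14%. That is fair, and it supports a ranking labelled as descriptive. It does not support the ranking as a finding on a primary hypothesis.

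Fourth, this is a pilot: "We will analyze the data of the study to find trends and to gather pilot data for preparing a future trial", and V.B ties success to compliance, dropout and adverse events. This limits the stakes.

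Finally, EMG, autonomic function and spasticity each have several measures, and no direction is given for autonomic change. V.A's regressions already need one summary variable per factor, but a direction for each would have to be added.

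**Conclusion.** The concern holds. The comparative half of the primary hypothesis has no analysis in V.A that estimates or tests it, and the exploratory regression does not fill the gap. How often this would mislead depends on the assumed correlations and on reading V.A as a ranking rule; the mismatch between hypothesis and analysis depends on neither. The point should be fixed, but the stakes are moderate: a wrong ranking would mainly misdirect the future trial. At 15 participants a direct comparison has useful power only if the rival correlations are near zero, so estimation is more realistic than a test.

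**What to change.** Either of two changes is enough.

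- In V.A, for each heart-rate outcome and with the factors coded in a stated common direction, report the EMG correlation minus each of the three rival correlations. Give a 90% confidence interval for overlapping dependent correlations (Fisher-z MOVER or bootstrap), present this as estimation, and base any statement that EMG is stronger only on these intervals.
- Or reword the comparison in I.A and V.B as a descriptive, exploratory ranking.

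The multiple regression can stay as the exploratory step it already is. Optionally, add to II.C that the 80% power does not cover the comparison between factors.

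The cost is a few lines of analysis on data already being collected, a stated direction for each factor, and some wording. No participants are added. The intervals will be wide, so the comparison will probably be inconclusive, which is acceptable in a pilot that looks for trends.
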